6.4. EARLY POSTOPERATIVE CHARACTERISTICS

N/A

6.5. POSTOPERATIVE CHARACTERISTICS

The analysis of the Postoperative data must be performed separately for each follow-up visit listed in table 4.4 in accordance to the following tables in this chapter. New Variables must be created individually for each follow-up visit.

Evaluation Variable / Question	Level of Measurement	Analysis Plan	Inclusion		
Postoperative Visit Form – Date of Visit			IR	FR	N/A
Date of Visit [dd.mmm.yyyy]:	Date/Time	None			X
Creation of variable Difference between Date of Surgery [dd.mmm.yyyy] and Date of "FU Visit" [dd.mmm.yyyy] In [] days [] (Variable(s): VISITID; VISNAME)	Quantitative, ratio	Case summary with number and percentage of valid cases/values, missing cases/values (if any) and total cases/values. Mean, median, interquartile range, maximum, minimum, standard deviation, 95% confidence interval for mean, Shapiro-Wilk Test.		X	

Table 6.5.1: Postoperative Visit Form – Date of Visit

Evaluation Variable / Question	Level of Measurement	Analysis Plan	Inclusion		
Postoperative Visit Form – ASES Shoulder Score			IR	FR	N/A
Q1 - Usual Work (Variable(s): USWORK)	Text, String	Listing of comments identified by subject code/ID			X
Q2 - Usual Sport/Leisure activity? (Variable(s): USSPRT)	Text, String	Listing of comments identified by subject code/ID			X
Q3 - Do you have shoulder pain at night? (Variable(s): PNIGHT)	Qualitative, nominal	Proportions, frequencies, column and row totals, missing proportion (if any).			X
Q4 - Do you take pain killers such as paracetamol (acetaminophen), diclofenac, or ibuprofen? (Variable(s): PNKLR)	Qualitative, nominal	Proportions, frequencies, column and row totals, missing proportion (if any).			X
Q5 - Do you take strong pain killers such as codeine, tramadol, or morphine? (Variable(s): CODTRMD)	Qualitative, nominal	Proportions, frequencies, column and row totals, missing proportion (if any).			X
Q6 - How many pills do you take on an average day? (Variable(s): PILLNUM)	Quantitative, ratio	Case summary with number and percentage of valid cases/values, missing cases/values (if any) and total cases/values. Mean, median, interquartile range, maximum, minimum, standard deviation, 95% confidence interval for mean, Shapiro-Wilk Test.			X
Q7 - Intensity of pain? (Variable(s): PAINC)	Quantitative, ratio	Case summary with number and percentage of valid cases/values, missing cases/values (if any) and total cases/values. Mean, median, interquartile range, maximum, minimum, standard deviation, 95% confidence interval for mean, Shapiro-Wilk Test.			X
Q8 - Is it difficult for you to put on a coat? (Variable(s): PUTCOAT)	Qualitative, Ordinal	Proportions, frequencies, column and row totals, missing proportion (if any).			X

Q9 - Is it difficult for you to sleep on the affected side? (Variable(s): DIFSLP)	Qualitative, Ordinal	Proportions, frequencies, column and row totals, missing proportion (if any).			X
Q10 - Is it difficult for you to wash your back/do up bra? (Variable(s): WASHBCK)	Qualitative, Ordinal	Proportions, frequencies, column and row totals, missing proportion (if any).			X
Q11 - Is it difficult for you manage toileting? (Variable(s): MNGTOIL)	Qualitative, Ordinal	Proportions, frequencies, column and row totals, missing proportion (if any).			X
Q12 - Is it difficult for you to comb your hair? (Variable(s): COMBHR)	Qualitative, Ordinal	Proportions, frequencies, column and row totals, missing proportion (if any).			X
Q13 - Is it difficult for you to reach a high shelf? (Variable(s): HIGHSHL)	Qualitative, Ordinal	Proportions, frequencies, column and row totals, missing proportion (if any).			X
Q14 - Is it difficult for you to lift 10lbs. (4.5kg) above your shoulder? (Variable(s): LIFT10)	Qualitative, Ordinal	Proportions, frequencies, column and row totals, missing proportion (if any).			X
Q15 - Is it difficult for you to throw a ball overhand? (Variable(s): BALLOV)	Qualitative, Ordinal	Proportions, frequencies, column and row totals, missing proportion (if any).			X
Q16 - Is it difficult for you to do your usual work? (Variable(s): DFWORK)	Qualitative, Ordinal	Proportions, frequencies, column and row totals, missing proportion (if any).			X
Q17 - Is it difficult for you to do your usual sport/leisure activity? (Variable(s): SPRACT)	Qualitative, Ordinal	Proportions, frequencies, column and row totals, missing proportion (if any).			X
ASES Pain Score [points] (Variable(s): PAINSC)	Quantitative, ratio	Case summary with number and percentage of valid cases/values, missing cases/values (if any) and total cases/values. Mean, median, interquartile range, maximum, minimum, standard deviation, 95% confidence interval for mean, Shapiro-Wilk Test.	X	X	
ASES Functioning Score [points] (Variable(s): FUNSCORE)	Quantitative, ratio	Case summary with number and percentage of valid cases/values, missing cases/values (if any) and total cases/values. Mean, median, interquartile range, maximum, minimum, standard deviation, 95% confidence interval for mean, Shapiro-Wilk Test.	X	X	
Total ASES Shoulder Score [points] (Variable(s): FINSCORE)	Quantitative, ratio	Case summary with number and percentage of valid cases/values, missing cases/values (if any) and total cases/values. Mean, median, interquartile range, maximum, minimum, standard deviation, 95% confidence interval for mean, Shapiro-Wilk Test.	X	X	

Table 6.5.2: Postoperative Visit Form – ASES Shoulder Score Tables List

Evaluation Variable / Question	Level of Measurement	Analysis Plan	Inclusion		
			IR	FR	N/A
Postoperative Visit Form – Range of Motion					
Flexion (Variable(s): FLEX)	Qualitative, nominal	Proportions, frequencies, column and row totals, missing proportion (if any).		X	
Abduction (Variable(s): ABDC)	Qualitative, nominal	Proportions, frequencies, column and row totals, missing proportion (if any).		X	

Extension (Variable(s): EXTN)	Qualitative, nominal	Proportions, frequencies, column and row totals, missing proportion (if any).		X	
External Rotation (Variable(s): EXROT)	Qualitative, nominal	Proportions, frequencies, column and row totals, missing proportion (if any).		X	
Internal Rotation (Variable(s): INTOR)	Qualitative, nominal	Proportions, frequencies, column and row totals, missing proportion (if any).		X	

Table 6.5.3: Postoperative Visit Form – ROM Tables List

Evaluation Variable / Question	Level of Measurement	Analysis Plan	Inclusion		
			IR	FR	N/A
Postoperative Visit Form – Radiographic Evaluation					
Implant dislocation (complete dislocation) (Variable(s): QA)	Qualitative, Nominal	Proportions, frequencies, column and row totals, missing proportion (if any).		X	
Periprosthetic fracture of the humerus (Variable(s): QB)	Qualitative, Nominal	Proportions, frequencies, column and row totals, missing proportion (if any).		X	
Periprosthetic fracture of the glenoid (Variable(s): QC)	Qualitative, Nominal	Proportions, frequencies, column and row totals, missing proportion (if any).		X	
Implant component dissociation (humeral head from humeral stem) (Variable(s): QD)	Qualitative, Nominal	Proportions, frequencies, column and row totals, missing proportion (if any).		X	
Radiologic signs of erosion of the glenoid (in hemiarthroplasty only) (Variable(s): QE)	Qualitative, Nominal	Proportions, frequencies, column and row totals, missing proportion (if any).		X	
Breakage of the humeral stem (Variable(s): QF)	Qualitative, Nominal	Proportions, frequencies, column and row totals, missing proportion (if any).		X	
Radiologic signs of breakage of the glenoid component (Variable(s): QG)	Qualitative, Nominal	Proportions, frequencies, column and row totals, missing proportion (if any).		X	
Radiologic signs of wear of the glenoid component (Variable(s): QH)	Qualitative, Nominal	Proportions, frequencies, column and row totals, missing proportion (if any).		X	
Radiologic signs of rotator cuff tear (superior/cranial migration) (Variable(s): QI)	Qualitative, Nominal	Proportions, frequencies, column and row totals, missing proportion (if any).		X	
Heterotopic ossification (Variable(s): QJ)	Qualitative, Nominal	Proportions, frequencies, column and row totals, missing proportion (if any).		X	
Radiolucency of the humerus (Variable(s): QK)	Qualitative, Nominal	Proportions, frequencies, column and row totals, missing proportion (if any).		X	
Radiologic signs of gross loosening of the humeral stem (Variable(s): QL)	Qualitative, Nominal	Proportions, frequencies, column and row totals, missing proportion (if any).		X	
Radiolucency of the glenoid (Variable(s): QM)	Qualitative, Nominal	Proportions, frequencies, column and row totals, missing proportion (if any).		X	
Gross loosening of the glenoid component (Variable(s): QN)	Qualitative, Nominal	Proportions, frequencies, column and row totals, missing proportion (if any).		X	
Non-union of lesser tuberosity osteotomy (Variable(s): QO)	Qualitative, Nominal	Proportions, frequencies, column and row totals, missing proportion (if any).		X	
Malunion of lesser tuberosity osteotomy (Variable(s): QP)	Qualitative, Nominal	Proportions, frequencies, column and row totals, missing proportion (if any).		X	
Other (Variable(s): QQ)	Qualitative, Nominal	Proportions, frequencies, column and row totals, missing proportion (if any). Listing of given description.		X	

Other description (Variable(s): DESC)	Qualitative, Nominal	Listing of given description.			X
Heterotopic ossification (modified BROOKER grading) (Variable(s): QS; QTG0; QTG1; GR1ZN; QTG2; GR2ZN; QTG3; GR3ZN; QTG4; GR4ZN; QTG5)	Qualitative, Nominal	Proportions, frequencies, column and row totals, missing proportion (if any).		X	
Radiolucent lines 2 mm or greater in ≥ 3 zones (Variable(s): QU)	Qualitative, Nominal	Proportions, frequencies, column and row totals, missing proportion (if any).		X	
Tilting ($> 5^\circ$) or subsidence (> 5 mm) of the stem (Variable(s): QV)	Qualitative, Nominal	Proportions, frequencies, column and row totals, missing proportion (if any).		X	
Thinning (“scalloping”) of the humeral cortex (Variable(s): QW; QX)	Qualitative, Nominal	Proportions, frequencies, column and row totals, missing proportion (if any). Listing of given description.		X	
Description of Radiolucency (Variable(s): QY)	Qualitative, Nominal	Proportions, frequencies, column and row totals, missing proportion (if any).		X	
If pegged glenoid component (Variable(s): QZ)	Qualitative, Nominal	Proportions, frequencies, column and row totals, missing proportion (if any).		X	
If keeled glenoid component (Variable(s): QAA)	Qualitative, Nominal	Proportions, frequencies, column and row totals, missing proportion (if any).		X	

Table 6.5.4: Postoperative Visit Form – Radiographic Evaluation Tables List

6.6. ANALYSIS OF CI ENDPOINTS

Evaluation Variable / Question	Level of Measurement	Analysis Plan					
Endpoints – Primary Endpoint							

Use variable Total ASES Shoulder Score 24 Months [points]: Based on the underlying distribution of the data and the result of the normality assessment, either the parametric one-sample t-test or the non-parametric one-sample sign test will be used to compare the 24 months postoperative ASES Shoulder Score results of the ReUnion TSA group against the lower maximum acceptable difference ($-\theta$) of 65.40 points.
 
The analysis of the primary endpoint will be part of the final report.
							

Table 6.6.1: Endpoints – Primary Endpoint Tables List

Evaluation Variable / Question	Level of Measurement	Recode and Analysis Plan	Inclusion		
Adverse Events – Time to (earliest) Device-Related Adverse Event / Incident			IR	FR	N/A
Creation of variable Difference between Date of Surgery [dd.mm.yyyy] and Date of First Device Related Adverse Event [dd.mm.yyyy] in days / (Variable(s): VISITDT; AEONSTDT)	Quantitative, ratio	Case summary with number and percentage of valid cases/values, missing cases/values (if any) and total cases/values. Mean, median, interquartile range, maximum, minimum, standard deviation, 95% confidence interval for mean, Shapiro-Wilk Test.		X	
Creation of variable Difference between Date of Surgery [dd.mm.yyyy] and Date of “most recent” Visit [dd.mm.yyyy] in days / (Variable(s): VISITDT)	Quantitative, ratio	N/A (Analyzed above), used for survivorship		X	

Create new variable “Grouping variable – First Device Related Adverse Event” (Variable(s): AEONSTDT)	Qualitative, nominal	- censored = survivors - events = first (earliest) Device Related Adverse Event		X	
Create new variable “Combined Time – First Device Related Adverse Event” (Variable(s): AEONSTDT)	Quantitative, ratio	- Use time between surgery and “most recent” visit for surviving subjects - Use time between surgery and first device related adverse event for subjects with device related adverse event		X	
Use variables “Combined Time – First Device Related Adverse Event” and “Grouping variable – First Device Related Adverse Event”	Qualitative, nominal Quantitative, ratio	Case summary with number and percentage of valid cases/values, missing cases/values (if any) and total cases/values. Kaplan-Meier survival analysis: subject ID, time, status, cumulative proportion, Kaplan-Meier estimate, standard error of KM estimate, number of cumulative events, number of remaining cases, mean for survival time with 95% confidence interval, survival graph, hazard graph.		X	

Table 6.6.2: Endpoints – Secondary Endpoint Time to (earliest) Device Related Adverse Event / Incident Tables List

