8.2. SECONDARY ENDPOINT

In addition to the principal endpoint, information on the following outcomes will be assessed up to 10 years after the index procedure:

Safety: Incidence of device-related intra-operative and post-operative AEs

Efficacy: Implant survivorship

9. Selection of Clinical Investigation Population

Subjects participating in this clinical investigation will be recruited from the investigator's standard subject population, where all subjects presenting for primary or revision total shoulder replacement will be evaluated for clinical investigation participation based on the eligibility criteria listed below.

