	95% Confidence Interval for Mean	Lower Bound	76,2372					
		Upper Bound	88,0828					
	Median	81,5000						
	Std. Deviation	8,27945						
	Minimum	64,00						
	Maximum	94,40						
	Interquartile Range	9,40						
								
Red line: Pooled mean ASES Blue lines: 95% CI of pooled mean ASES Black line: Pooled median pooled ASES Box: Interquartile Range Green Line: Pooled mean ASES minus pooled std. dev. ASES (16.76) $82.16 - 16.76 = \mathbf{65.40 \text{ points}}$								
Acceptance Criteria for Sample Size Calculation								
Significance Level (α)	0.05 (5%)							
Power (1- β)	0.80 (80%)							
Confidence Interval (CI)	0.95 (95%)							
Tails	2							
Path	Non-inferiority – ReUnion TSA (A) \geq Benchmark (B, explorative meta-analysis in this document)							
Hypotheses Pair	Null (H_0)	$A - B < -\theta$						
	Alternative (H_1)	$A - B \geq -\theta$						
Benchmark Timepoint	24 months postoperative							
Benchmark n (sources)	10							
Benchmark Mean	82.16 (pooled mean ASES [points])							
Benchmark Std. Dev.	16.76 (pooled std. dev. ASES [points])							
Benchmark Value Non-Inferiority Margin (- θ)	Pooled mean ASES minus pooled std. dev. ASES (16.76) $82.16 - 16.76 = \mathbf{65.40 \text{ points}}$							
Software Used	IBM SPSS Sample Power V3.0							
IBM SPSS Sample Power Output								
One goal of the proposed clinical investigation is to test the null hypothesis that the population mean is 82.16 points. The criterion for significance (alpha) has been set at 0.05. The test is 2-tailed, which means that effects in both directions will be interpreted. With the proposed sample size of 10 cases, the clinical investigation will have power of 80.3% to yield a statistically significant result. This computation assumes								

that the population from which the sample will be drawn has a mean of 82.16 points with a standard deviation of 16.76 points. The observed value will be tested against a theoretical value (constant, non-inferiority margin) of 65.40 points.

IBM SPSS Sample Power Output – Screenshot

Estimated overall drop-out rate is 56% which leads to the requirement of enrolling additional 6 subjects into the clinical investigation.

Sample Size	Number of subjects to be enrolled: 16 subjects (rounded up to 20 subjects)
Overall Sample Size (multiplied by number of indications (=5)	100 subjects

Table 3.2: Sample Size Justification

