6.7.3. Reoperation Surgery

For analysis of the time to the reoperation surgery, the Kaplan-Meier method will be used. The times between surgery and the most recent or last available assessment per subject will be used together with the times between surgery and the date of reoperation (earliest reoperation in case that one subject experienced more than one reoperation). This analysis is part of the final report.

Evaluation Variable / Question	Level of Measurement	Recode and Analysis Plan
Adverse Events / Reoperation Surgery		
Creation of variable Difference between Date of Surgery [dd.mm.yyyy] and Date of First Reoperation [dd.mm.yyyy] in [] days [] (Variable(s): VISITDT)	Quantitative, ratio	Case summary with number and percentage of valid cases/values, missing cases/values (if any) and total cases/values. Mean, median, interquartile range, maximum, minimum, standard deviation, 95% confidence interval for mean, Shapiro-Wilk Test.
Creation of variable Difference between Date of Surgery [dd.mm.yyyy] and Date of “most recent” Visit [dd.mm.yyyy] in [] days [] (Variable(s): VISITDT)	Quantitative, ratio	N/A (Analyzed above), used for survivorship
Create new variable “Grouping variable - First Reoperation” (Variable(s): VISITDT)	Qualitative, nominal	- censored = survivors - events = first (earliest) Reoperation
Create new variable “Combined Time - First Reoperation” (Variable(s): VISITDT)	Quantitative, ratio	- Use time between surgery and most recent visit for surviving subjects - Use time between surgery and first reoperation for subjects with reoperation(s)
Use variables “Combined Time - First Reoperation” and “Grouping variable - First Reoperation”	Qualitative, nominal Quantitative, ratio	Case summary with number and percentage of valid cases/values, missing cases/values (if any) and total cases/values. Kaplan-Meier survival analysis: subject ID, time, status, cumulative proportion, Kaplan-Meier estimate, standard error of KM estimate, number of cumulative events, number of remaining cases, mean for survival time with 95% confidence interval, survival graph, hazard graph.

Table 6.7.3.1: All Assessments – Reoperation Surgery Tables List

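### The 10-year device-event and reoperation curves do not code death without an event, and no planned summary estimates 10-year incidence with death as a competing event

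*SAP*

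**What the plan says.** Protocol 8.2 lists the incidence of device-related adverse events (safety) and implant survivorship (efficacy) as secondary endpoints and states that "information on the following outcomes will be assessed up to 10 years after the index procedure". Protocol 11.3.3 and SAP 3.1.2 name Kaplan-Meier for time to the earliest device-related event. Protocol 11.3.3 and SAP 6.7.3 name it for time to a secondary procedure or reoperation.

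SAP Table 6.6.2 defines the status variable for the first of these as "censored = survivors - events = first (earliest) Device Related Adverse Event". Table 6.7.3.1 has the same two statuses for reoperation, and its time rule for those without the event is "Use time between surgery and most recent visit for surviving subjects". Neither table mentions a subject who dies before having the event.

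Three other places bear on this:
- Protocol 9.3 (iv) says that death is not a device failure unless the device caused it, and that data up to death enter the final analysis.
- SAP 6.7.2 gives mortality its own Kaplan-Meier analysis and uses the date of death (DOSEDD).
- SAP 6.1 tabulates adverse events and reoperations as proportions and frequencies.

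No competing-risk estimate appears in either document.

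**The concern.** A subject who has died can no longer have a device event or a reoperation. If that subject is censored like someone who is alive and merely not seen again, Kaplan-Meier estimates the event risk as though nobody died. That answers a question about the implant. It does not answer how many of the treated subjects have an event within 10 years, which is the ordinary meaning of the incidence endpoint.

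There is also a coding gap. In the mortality table (SAP 6.7.2) a survivor is someone who is alive. The same word in Tables 6.6.2 and 6.7.3.1 has to mean someone without the event. Two analysts could code event-free deaths differently, and the choice moves the estimate. At stake are the 10-year safety figures; no test depends on them.

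**Working it through.** **The plan's own figures.** The plan states no figure for these curves. The only computed design figure is for the primary test: "the clinical investigation will have power of 80.3% to yield a statistically significant result". It reproduces. For a one-sample t-test with n = 10, difference 82.16 - 65.40 = 16.76, SD 16.76 and two-sided alpha 0.05, the non-centrality is sqrt(10) x 16.76/16.76 = 3.16 on 9 df, and power is 80.31%. It plays no part in what follows.

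**Inputs from the documents.** Enrolment of 100 (SAP 3.2), follow-up of 10 years (Protocol 8.2) and overall drop-out of 56% (SAP 3.2; the share due to death is not given).

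**Assumed inputs.** The documents give no event or death rate. I take a 10-year 1-KM of 5%, 10% or 20%, and 10-year mortality of 10% to 40%.

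**Formula.** Let p be the 10-year 1-KM with deaths censored and m the 10-year mortality. With constant, independent hazards, e = -ln(1-p)/10 and d = -ln(1-m)/10. The cumulative incidence with death as a competing event is

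CIF = e/(e+d) x [1 - exp(-10(e+d))].

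Example with p = 10%, m = 30%: e = 0.01054, d = 0.03567, and exp(-10(e+d)) = 0.90 x 0.70 = 0.63. So CIF = (0.01054/0.04620) x 0.37 = 8.4%, and the excess of 1-KM is 1.6 points.

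| 1-KM | m = 10% | m = 20% | m = 30% | m = 40% |
|---|---|---|---|---|
| 5% | 0.3 | 0.5 | 0.8 | 1.1 |
| 10% | 0.5 | 1.0 | 1.6 | 2.1 |
| 20% | 1.0 | 2.0 | 3.1 | 4.2 |

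(Entries are 1-KM minus CIF, in percentage points. In relative terms the excess runs from about 5% at m = 10% to 27% at m = 40%.)

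**Early events.** If half of the cumulative event hazard falls in the first 3 months, the excess is roughly halved. For p = 10%, m = 30% it is 0.8 points; for p = 20%, m = 40% it is 2.1.

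**Sampling error and coding choice.** I simulated 100 subjects, with 4,000 runs per scenario. The 56% is assumed to be total 10-year loss including deaths.

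| Quantity | p = 10%, m = 30% | p = 20%, m = 30% |
|---|---|---|
| True cumulative incidence | 8.4% | 16.9% |
| Mean 1-KM, censored at death | 10.0% | 20.1% |
| Mean 1-KM, censored at last visit | 10.4% | 20.8% |
| Mean 1-KM, event-free deaths dropped | 11.5% | 22.8% |
| Simple proportion of all enrolled | 6.8% | 13.9% |
| SD of 1-KM (censored at death) | 3.8 points | 5.0 points |

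With censoring at death, the excess relative to the SD is 1.6/3.8 = 0.4 in the first scenario and 3.1/5.0 = 0.6 in the second. Censoring at the last visit, or dropping the deaths, raises the estimate further. The simple proportion errs the other way, because events after loss to follow-up are not seen.

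**The case against.** The strongest reply is that nothing here is an error. SAP 6.6 lists survival-scale outputs (Kaplan-Meier estimate, mean survival time, survival and hazard graphs) and nowhere calls 1-KM an incidence. Implant survivorship is itself a named endpoint, and Kaplan-Meier is a legitimate net measure of it if death is independent of device failure. Deaths are visible in their own analysis. There is no test or threshold on these curves, and SAP 4.2 sets no stopping rules. All of this stands, and it limits the point to a reporting improvement.

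Four stronger readings are tempting, and the documents do not support them:
- *That subjects who die event-free get no follow-up time.* The text of SAP 6.7.3 uses the last available assessment for each subject, and Protocol 9.3 keeps data up to death. Censoring at the last assessment is the natural reading, although the tables should say so.
- *That the excess lies in the subjects who die with the implant in place.* It lies in the estimate for the whole cohort.
- *That the published incidence will certainly be materially overstated.* This needs a reader to convert the curve to 1-KM and take it as actual risk, and the size rests on rates that the documents do not give.
- *That comparison with other series is distorted.* The only planned external comparison is the 24-month ASES score.

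The reply does not remove the gap. Incidence is a named endpoint, and under heavy loss to follow-up the tabulated proportions are not an adequate estimate of it.

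**Conclusion.** The point holds as a cheap improvement of low severity. Death without an event is uncoded in both tables, and no planned summary estimates 10-year incidence well: 1-KM is too high when event-free deaths occur, and the simple proportion is too low under loss to follow-up. The direction of the 1-KM excess does not depend on assumed rates. Its size does: about 0.3 to 4 points over the range above under constant hazards, about half that if events cluster early, and usually less than one standard error at n = 100. The net reading of Kaplan-Meier also assumes that death is independent of device failure. The primary endpoint and its conclusion are not affected.

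**What to change.** In Tables 6.6.2 and 6.7.3.1, use three statuses:
- 0 = alive and event-free, censored at the last assessment;
- 1 = event, at the event date;
- 2 = death without an event, at the date of death (DOSEDD).

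State how a device-caused death, which Protocol 9.3 treats as a device failure, is coded in each table; the reoperation table has no place for it now. Report the cumulative incidence function with its 95% CI, with death as the competing event, as the incidence result for each endpoint. Keep the Kaplan-Meier curve beside it, labelled as net survivorship. If nothing else changes, at least define the status and time of event-free deaths; that step depends on no assumed rate.

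The cost is one extra status code and one extra estimate per endpoint, from data already collected. The estimate may need software other than the base SPSS Kaplan-Meier procedure, and SAP 4.5 allows other standard packages. The change does not correct for loss to follow-up that is related to outcome; that limitation applies to either estimator.
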